1.1 Cystic fibrosis

Cystic fibrosis is caused by mutations in the *CFTR* gene with an autosomal recessive inheritance. It is a rare disease with a prevalence of 1-9/100,000 in Europe. The *CFTR* mutations result in a dysfunctional chloride channel that affects secretion from all exocrine glands.

The disease is chronic and generally progressive, with onset usually occurring during early childhood or, occasionally, at birth (meconium ileus). Virtually any internal organ may be involved but the principle manifestations concern the breathing apparatus (chronic bronchitis), pancreas (pancreatic insufficiency, adolescent diabetes and occasionally pancreatitis) and, more rarely, the intestine (stercoral obstruction) or liver (cirrhosis). The most common form of cystic fibrosis is associated with respiratory symptoms, digestive problems (steatorrhea and/or constipation) and staturponderal growth anomalies. Mortality and morbidity depend on the extent of bronchopulmonary involvement. Male sterility is a constant feature. Late-onset forms, which are usually only mild or monosymptomatic, have also been reported.

Diagnosis is suspected on the basis of sweat test results (chloride concentration above 60 mmol/L) and is confirmed by identification of a *CFTR* mutation. Neonatal testing has been widely available since the end of 2002 and leads to diagnosis in 95% of cases.

Classical treatment of cystic fibrosis is mainly symptomatic, revolving around bronchial drainage, antibiotics for respiratory infections, pancreatic analysis and administration of vitamins and calorific supplements for digestive and nutritional problems. These cost-effective treatments have significantly improved the prognosis for cystic fibrosis patients: in the 1960's the majority of patients died before 5 years of age, whereas the current average life-span exceeds 35 years and life-expectancy is 40 years.

1.2 Microbial involvement in CF

The lung of CF patients is often affected by recurrent infections and colonized by *Pseudomonas aeruginosa* that form a viscous biofilm. Recent studies describe a complex microbiome in patients with cystic fibrosis, and common threads have emerged across studies in the relationships observed between features of the respiratory microbiome and clinical outcomes. CF airway microbial communities were shown to be relatively stable during periods of clinical stability, but differ substantially between patients [1]. See following Figure 1. Most studies to date have focused on bacterial members of the respiratory

microbiome, but some recent investigations have also begun to characterize fungal and viral communities in CF [2, 3].

[figure not shown]

Figure 1 Baseline community structure. Bray-Curtis-based nonmetric multidimensional scaling plot showing daily sputum samples from four study subjects (subject A is red; subject B is green; subject C is black; subject D is blue), collected during clinically stable periods. Pairs of other symbols in gray are same sample replicate controls from subject A as described in Methods.

Taken from [1]

Although studies of respiratory microbiota have dominated CF microbiome studies, gastrointestinal complications of CF are a significant cause of disease morbidity, and problems beyond pancreatic insufficiency are often difficult to manage. Thus recently, investigations have also begun to characterize and analyze relationships between gastrointestinal bacterial microbiota, clinical disease markers, and profiles of airway bacterial community composition ([4, 5]; reviewed in [6]). Our knowledge on the relation of the intestinal and respiratory microbiome in CF is still very limited, but has great potential for biomarker discovery.

In CF, antibiotic therapy given in purpose to limit lung damage by bacterial colonization and infection, is a mainstay of therapy. Changes in respiratory and intestinal microbiome composition and diversity and the interrelationship between them are still to be elucidated.

1.3 Modern CF therapy

Since recently, medication is available that directly targets the impaired CFTR function. Depending on the type of mutation, the respective substances are called CFTR-potentiators or –correctors. In 2011, two large clinical studies (STRIVE und ENVISION) showed that the CFTR-potentiator Ivacaftor (trade name Kalydeco®) significantly improves clinical

parameters in patients with the rare G551D mutation [7, 8], and with to date eight other rare CFTR mutations.

Patients with the most common *CFTR* mutation Phe508del (= F508del) benefit from a therapy with a combination of the CFTR-corrector Lumacaftor with the *CFTR*-potentiator Ivacaftor, as shown in the TRANSPORT und TRAFFIC studies [9]. In Germany this combination is approved for CF since Nov 2015 (trade name **Orkambi**®). It improves CFTR function and thus influences secretion, e.g. in the lung and gut of patients.

For Ivacaftor alone, a small study comprising three patients described a modified respiratory microbiome with a trend towards higher diversity [10]. Based on this, we hypothesize that the treatment with **Kalydeco or Orkambi**® will influence the composition of the CF microbiome in eligible patients towards a healthy and stable high-diversity state.

2. Aims

Our study targets the influence of standard CF therapy on the CF microbiome. The respiratory and intestinal microbiome and their interrelationship will be characterized in a longitudinal study design. The observed changes will be correlated to functional (FEV1, body weight, laboratory parameters) und quality of life (CFQ-R, Kiel-Q) parameters We aim at the detection of significant changes in microbial parameters in the respiratory tract and in the gut following medical therapy (e.g. antibiotics, CFTR modulators). The microbial composition will further be correlated to treatment response, in order to discover potential microbial biomarkers.

3. Study design

3.1 Participants and clinical data

The study comprises analysis of clinical parameters and microbiome and 8 time points. Patients are recruited from the adult cf centre at the University Hospital of Schleswig Holstein, Campus Kiel, Innere Medizin I. Eligible patients are patients with a confirmed diagnosis of cystic fibrosis (sweat chloride >60mmol/l and /or 2 cf causing mutations in the CFTR gene) and the ability to give informed consent .

All participants receive a questionnaire at each time point of sampling that will either be filled in by themselves or by a study nurse via a telephone interview. Clinical data is collected by the medical study team from standard health records and via a questionnaire. From clinical data CF-genotype, microbial status concerning chronic infection with *Pseudomonas*

aeruginosa and other bacteria, height and weight, current medication, presence and frequency of exacerbations, lung function parameters (e.g. FEV₁, FVC, MEF 25, MEF 75-25), full blood count, C reactive protein, liver function tests (AST, ALT, GGT, ALP, TBil), creatin kinase, calprotectin and elastase will be enrolled. The questionnaires contain i) basic items, like age and body weight, ii) items related to the CF phenotype and the clinical outcome, like quality-of-life, lung function and other medical complaints, and iii) items that relate to the microbiome, like food intake or other medication.

3.2 Recruitment and biosampling

Biosampling will be performed at each time point with a tolerance of three days. For stool sampling the participants will receive sampling tubes that will be sent back by mail. Respiratory samples will either be taken during the visit by the medical study team or by the participants at home. At each time point two stool samples, one sputum sample and one throat swab will be collected.

Biosampling is performed in an anonymized fashion. Sample preparation and the generation of molecular profiles is conducted at the IKMB and will be managed by [name]. The IKMB staff receives samples and phenotypes without any information that allows the identification of individual study participants, so that data protection policies will be fulfilled within the entire study.

3.3 Phases

The study course is subdivided in two phases. The first 3 samples collected at timepoints "0", "2" and "4" will generate a baseline for analysis of the comparison with following samples.

[figure not shown]
4. Molecular profiling and data analysis

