4.3 Statistical analysis of microbial profiles and modeling of microbial changes

The obtained sequences provide information of the composition of the microbial community in each sample at a qualitative and quantitative level. As the primary outcome the diversity within one sample (α -diversity) will be determined that can be expressed in various indices, e.g. Chao1 or Shannon index, and changes in α -diversity will be calculated (Δdiv). In addition, the specific composition of the microbiome profiles will be analyzed. Respiratory and intestinal profiles will first be investigated separately, and will be then be analyzed for a possible correlation. The following procedures and tests will be conducted in the given order:

- 1) Calculation of changes in α -diversity indices for each sample (Δdiv ; “baseline” vs. “follow-up”) and comparison of diversities correlated to treatment characteristics of the patients (e.g. antibiotic versus non-antibiotic, CFTR modified versus non-CFTR modified).
- 2) We hypothesize that the α -diversity in patient’s microbiome will change in response to external stimuli (E.g.: Decrease in response to antibiotic therapy? Increase in response to CFTR Modification?). In all patients indices of the three time points “baseline” will be summarized and used for the calculation of the α -diversity change. A non-parametric test will be applied to test, if there is are significant changes in α -diversity in response the initiation of antibiotic oder CFTR modifying treatment.
- 3) Fitting of a statistical model for the change in α -diversity in patient`s microbiome.
- 4) Correlation of the α -diversity with therapy response in as well as over the entire course of the study.
- 5) Analysis of the abundance of specific bacteria or fungi over the time course using a zero-inflated model
- 6) Comparison of the composition of the obtained microbial profiles (β -diversity) between timepoints and patient’s characteristic groups by PCoA (multiple scaling analysis)
- 7) Correlation of microbial parameters (changes in α -diversity or specific organisms) of respiratory and intestinal samples

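### The fixed 0/2/4 baseline is used to test response to treatment initiation, but nothing in the text keeps those samples free of the treatment under test, so the measured change can be diluted

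*Protocol*

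**What the plan says.** Section 3.3 states that "The study course is subdivided in two phases" and that the first three samples, at time points 0, 2 and 4, "will generate a baseline for analysis of the comparison with following samples". The rest of that section is a figure that is missing from the text reviewed.

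Section 4.3 makes alpha-diversity the primary outcome. Step 1 calculates its change from baseline to follow-up and adds a "comparison of diversities correlated to treatment characteristics of the patients", for example antibiotic against no antibiotic. Step 2 applies the baseline to everyone ("In all patients indices of the three time points" are summarised, without saying whether by mean or median). It then uses a non-parametric test for change "in response the initiation of antibiotic oder CFTR modifying treatment". The hypothesised directions are put as questions: "Decrease in response to antibiotic therapy", and an increase with CFTR modification.

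On who enters and what is recorded, section 3.1 says "Eligible patients are patients with a confirmed diagnosis of cystic fibrosis" who can consent. It sets no condition on current antibiotics or modulators. Current medication is taken from the health records, and "All participants receive a questionnaire at each time point of sampling", with items on other medication. Section 1.2 describes antibiotics as a mainstay of CF care. Section 4.4 lists medication among the confounders to be included and bases the chance of detection on 45 patients.

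**The concern.** The baseline is tied to the study calendar, while the event under test is tied to each patient's own treatment start. The text does not connect the two. In a population where antibiotics are routine and eligibility does not exclude current treatment, some of the 0/2/4 samples may already be exposed. The change is then measured from a partly treated baseline.

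The primary outcome is at stake. A weak or null result could reflect when treatment happened to start rather than the absence of an effect. Patients already on a modulator at time 0 have no pre-treatment sample and carry no information about its initiation, yet step 2 as worded does not separate them. The within-patient initiation test therefore draws on those who start during the study, not on all 45. Non-starters contribute as comparators in step 1.

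**Working it through.** The protocol gives no effect size, standard deviation, significance level or power, so there is no figure of its own to reproduce.

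**Inputs from the protocol:** 8 time points (3.1), of which 3 are baseline (3.3), leaving 8 − 3 = 5 for follow-up; one summary of the three baseline values in all patients (4.3, step 2). **Assumed:** the summary is a mean, unless stated otherwise below.

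**Lasting effect, k of 3 baseline samples exposed.** Captured share = 1 − k/3.
- Start between points 2 and 4 (k = 1): 1 − 1/3 = 67%
- Start between points 0 and 2 (k = 2): 1 − 2/3 = 33%
- Already treated at time 0 (k = 3): 0%
- Start after point 4 (k = 0), on-treatment follow-up samples: 100%

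With a median instead of a mean, the captured shares for k = 1, 2, 3 are 100%, 0% and 0%.

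**Later antibiotic course, each baseline sample exposed with probability p (assumed).** If exposure lowers a sample by d, the expected baseline falls by p·d, so the captured share is 1 − p. The share of patients with at least one exposed baseline sample, if exposures are independent, is 1 − (1 − p)³.

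| p | captured | at least one exposed |
|---|---|---|
| 10% | 90% | 1 − 0.9³ = 27% |
| 20% | 80% | 1 − 0.8³ = 49% |
| 30% | 70% | 1 − 0.7³ = 66% |

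**Simulated power.** Assumptions: 20 initiators, effect −0.8 within-patient SD, signed-rank test at two-sided 0.05, on-treatment follow-up samples only, nobody already treated at time 0. The fixed 0/2/4 baseline is compared with a baseline aligned to the start.

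| Lasting effect: when treatment starts | Mean change, fixed vs aligned | Power, fixed vs aligned |
|---|---|---|
| Just after point 4 | no bias | above 99% both |
| Spread over follow-up | no bias | 96% vs 98% |
| Spread over all seven gaps | −0.69 vs −0.80 | 90% vs 97% |
| All inside the baseline | −0.40 vs −0.80 | 61% vs 94% |

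The two diluted means follow by arithmetic. Over seven equally likely gaps the average capture is (1/3 + 2/3 + 5)/7 = 6/7, and 6/7 × 0.8 = 0.69. For starts inside the baseline it is (1/3 + 2/3)/2 = 1/2, and 1/2 × 0.8 = 0.40.

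For one antibiotic course in follow-up with p = 10, 20 and 30%, and no carry-over, power is 73, 61 and 51% with the fixed baseline. It is 80, 77 and 75% when exposed baseline samples are left out.

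**Direction of the change.** Suppose a transient course lowers one baseline sample by d and has worn off by follow-up. An unexposed later sample then reads +d/3 = +0.33d, and a later exposed sample reads −d + d/3 = −0.67d. For the group average, let a fraction f of patients have such a course covering m baseline samples, and let the rest start in follow-up and stay affected. The average is −(1 − f)d + f·d·m/3, which is zero at f = 3/(3 + m): 75%, 60% and 50% for m = 1, 2, 3.

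**The case against.** The strongest reply is that the second phase is shown only in a figure that could not be seen. It may place modulator initiation after point 4, and the baseline and follow-up wording in 4.3 reads naturally that way. If so, and the baseline is unexposed, there is no loss. This stands for modulators, and the point is conditional there. It is much weaker for antibiotics, because a schedule is unlikely to fix the timing of as-needed courses.

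A second reply is that medication is recorded and named as a confounder, and that step 3 of 4.3 fits a model for the change in which exposure could be adjusted for. That helps if the model uses exposure at each sample, including the baseline ones. It does not alter the step 2 test, where the fixed baseline is already built into the change.

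A third is that initiator definitions and exposure coding commonly belong in the SAP, which was not available here. This is true of the detail. The protocol itself, however, states the baseline rule, applies it to all patients and uses it for this test.

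A reader might also infer that the plan would reverse the sign of the treatment effect. The documents do not support that. A lasting effect is only shrunk. Reversal is limited to unexposed later samples of patients whose transient course fell in the baseline, and those samples do not themselves test an initiation. Under the assumptions above, the group average would change sign only if more than about half to three quarters of patients had such courses. The protocol gives no antibiotic frequency from which to judge that.

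**Conclusion.** The point holds as a risk of dilution in the primary-outcome test of treatment initiation. It is firm for as-needed antibiotic courses and conditional on the unseen figure for modulators. A lasting effect is captured at 67% or 33% when one or two baseline samples are exposed, and a later antibiotic effect at 1 − p. The loss is nil or small when starts fall after point 4 and the baseline is unexposed. It is substantial only when many starts or courses fall among points 0 to 4.

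The fractions are exact for a mean baseline. The power figures rest on assumed numbers of starters, effect size, start times and exposure rates, none of which the protocol gives, so they show a range rather than a forecast. The case for change is that the improvement is cheap, not that the trial is shown to fail.

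**What to change.** In 4.3, steps 1 and 2, for the initiation test only:
- Define baseline as each patient's samples that precede the first recorded use of the treatment under test and are not exposed to it. Define follow-up as the exposed samples from then on.
- Code antibiotic and modulator exposure for every sample from the medication records and the questionnaire given at each time point.
- Do not count patients already on a modulator at time 0 as initiators of it; describe them separately.

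Keep 0/2/4 as the baseline for the general time course. State in the text of 3.3 how treatment initiation relates to the two phases, so that the reader need not rely on the figure. In 4.4, say that the within-patient initiation test rests on the patients who start during the study, not on all 45.

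The cost is wording and coding; no new visits or samples are needed. The initiation test will have fewer patients, because those without an unexposed sample before first use drop out of it. Baselines will be unequal and sometimes a single sample, in data that 4.4 itself describes as highly variable. Section 3.1 lists current medication but not start dates, so exposure may be known only to the nearest sample.

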4.1 Sample preparation

All collected samples will be processed at the IKMB according to established protocols. DNA will be isolated from stool and respiratory samples and used for the generation of microbial profiles. In addition, the isolated DNA samples can be used for all established sequencing application. A second stool sample will be used to measure the intestinal inflammatory marker Calprotectin and Elastase-1, in order to document intestinal and pancreatic involvement. Both methods are applied in the routine clinical setting, and are thus standardized and well established.

4.2 Microbial profiling by next generation sequencing (NGS)

Both bacterial and fungal profiles will analyzed within the study. The characterization of bacterial profiles is conducted by sequencing the *16S rRNA* gene, the so-called *16S DNA*, which is in parts highly variable and present in all bacterial and archaeal organisms. The 16S analysis by NGS is well established allows microbial profiling down to the genus level at a qualitative and quantitative level.

According to established protocols [11], the V1-V2 region of the *16S rDNA* of the extracted DNA is amplified in a sequence-specific PCR reaction. The PCR products are then normalized and a maximum of 384 samples are then pooled for sequencing with the Illumina MiSeq system.

For fungal profiling the highly variable *ITS1* and *ITS2* gene regions will be amplified and processed as described for bacterial profiling. For both bacteria and fungi the

identification of the corresponding microorganisms is conducted by the comparison of the obtained sequences to public sequence databases.

[figure not shown]
4.3 Statistical analysis of microbial profiles and modeling of microbial changes

The obtained sequences provide information of the composition of the microbial community in each sample at a qualitative and quantitative level. As the primary outcome the diversity within one sample (α -diversity) will be determined that can be expressed in various indices, e.g. Chao1 or Shannon index, and changes in α -diversity will be calculated (Δdiv). In addition, the specific composition of the microbiome profiles will be analyzed. Respiratory and intestinal profiles will first be investigated separately, and will be then be analyzed for a possible correlation. The following procedures and tests will be conducted in the given order:

- 1) Calculation of changes in α -diversity indices for each sample (Δdiv ; “baseline” vs. “follow-up”) and comparison of diversities correlated to treatment characteristics of the patients (e.g. antibiotic versus non-antibiotic, CFTR modified versus non-CFTR modified).
- 2) We hypothesize that the α -diversity in patient’s microbiome will change in response to external stimuli (E.g.: Decrease in response to antibiotic therapy? Increase in response to CFTR Modification?). In all patients indices of the three time points “baseline” will be summarized and used for the calculation of the α -diversity change. A non-parametric test will be applied to test, if there is are significant changes in α -diversity in response the initiation of antibiotic oder CFTR modifying treatment.
- 3) Fitting of a statistical model for the change in α -diversity in patient`s microbiome.
- 4) Correlation of the α -diversity with therapy response in as well as over the entire course of the study.
- 5) Analysis of the abundance of specific bacteria or fungi over the time course using a zero-inflated model
- 6) Comparison of the composition of the obtained microbial profiles (β -diversity) between timepoints and patient’s characteristic groups by PCoA (multiple scaling analysis)
- 7) Correlation of microbial parameters (changes in α -diversity or specific organisms) of respiratory and intestinal samples

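### Does the primary diversity test treat repeated samples from one patient as independent and so lose control of its type I error?

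*Protocol*

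**What the plan says.** Section 4.3 of the protocol makes α-diversity within a sample the primary outcome and lists seven analysis steps in order.

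- Step 1 calculates changes in "diversity indices for each sample", contrasting baseline with follow-up, and compares them by the patients' treatment characteristics (antibiotic or not, CFTR modified or not).
- Step 2 says that, in all patients, "indices of the three time points “baseline” will be summarized and used for the calculation of the" change. It continues: "A non-parametric test will be applied to test, if there is are significant changes in" α-diversity after antibiotic or CFTR-modifying treatment is started. The test is not named.
- Step 3 fits a statistical model for the change, of unstated type.

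On the number of samples, section 3.1 states: "The study comprises analysis of clinical parameters and microbiome and 8 time points". Section 3.3 divides the study into two phases and assigns the first three samples to baseline. Section 4.4 gives 45 patients. No significance level is stated.

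**The concern.** Taken literally and in sequence, the text defines a change for every sample, summarises only the baseline, and then tests. Nothing says that the follow-up samples are summarised. Eight time points less three baseline samples leaves five, so each patient could contribute five changes that all subtract the same baseline value.

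The usual signed-rank and rank-sum tests assume independent observations. Five changes that share a baseline are positively correlated even if the samples themselves vary independently around a stable patient level. Any patient-specific shift after baseline adds to that correlation. A test run on 45 × 5 = 225 values would overstate the information, which comes from 45 patients. At stake is the false-positive rate of the study's main hypothesis test.

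**Working it through.** The protocol gives no significance level, power or sample-size calculation, so there is no figure of its own to reproduce. The check asks how large the error would be under pooling, and whether the text requires pooling.

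**Inputs from the protocol.** 8 time points (section 3.1); 3 baseline samples (section 3.3), hence m = 8 − 3 = 5 follow-up samples; 45 patients (section 4.4).

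**Assumptions.** Two-sided α = 0.05; the baseline summary is a mean; samples have equal variance σ² and are independent around a stable patient level.

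**Correlation from the shared baseline.**
- Var(change) = σ² + σ²/3 = 4σ²/3
- Cov(two changes, same patient) = σ²/3
- ρ = (1/3)/(1 + 1/3) = 0.25

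**Error if all changes are pooled.**
- Design effect = 1 + (m − 1)ρ = 1 + 4 × 0.25 = 2.0
- Actual α = 2[1 − Φ(1.96/√2.0)] = 16.6%

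**Dependence on the number of follow-up samples pooled (ρ = 0.25).**

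| m | Design effect | Actual α |
|---|---|---|
| 1 | 1.00 | 5.0% |
| 2 | 1.25 | 8.0% |
| 3 | 1.50 | 11.0% |
| 4 | 1.75 | 13.8% |
| 5 | 2.00 | 16.6% |

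**Simulation under no effect** (45 patients, 3 + 5 samples, 4000 runs).

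| Analysis | Type I error |
|---|---|
| All changes pooled, rank-sum, exposure fixed within patient (splits 22/23, 15/30, 10/35) | 16.0–16.3% |
| All changes pooled, signed-rank | 15.6–16.5% |
| Pooled, with patient-level follow-up shift of SD 0.5σ | about 21% |
| Pooled, with patient-level follow-up shift of SD 1.0σ | about 28% |
| Pooled, rank-sum, exposure varying at random between a patient's samples | 4.9% |
| One mean change per patient, rank-sum | 4.5–5.5% |
| One mean change per patient, signed-rank | 5.0–5.2% |

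A separate simulation of one test per follow-up time point, in which each patient enters once, gave 4.5–5.2%, even with patient-level shift. Multiplicity across time points is another matter. The shift SDs of 0.5σ and 1.0σ are illustrative; the protocol gives no value.

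**What the text commits to.** The per-sample phrase in step 1 governs a calculation. Step 2, which holds the test, is worded in terms of patients and names neither a test nor a unit. Step 1 states its contrast as baseline against follow-up, and section 3.3 has two phases; both fit one contrast per patient. The phrase may also refer to each type of material: section 3.2 collects stool, sputum and a throat swab at every time point, and section 4.3 analyses respiratory and intestinal profiles separately at first. No sentence says that the changes are pooled or treated as independent.

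**The case for a change.** The strongest case for a change is that section 4.3 is more than an outline. It fixes the outcome, the level at which the change is calculated, the baseline rule, the class of test and the order of steps. Only the baseline is said to be summarised, and the grouping is described as a characteristic of patients, which is the setting where pooling does harm. An analyst following it word for word could inherit the error, and the unspecified model in step 3 would not repair the test in step 2.

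The conditional arithmetic in this stands: pooling all five changes would give about 16%. It also stands that the unit of the test is not written down.

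Three parts do not stand.

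- The word-for-word reading is one of several, and the valid ones are at least as natural.
- The 16% is not a floor. It needs all five follow-up samples, an exposure fixed within the patient or a one-sample test of change, and an assumed α of 0.05. Step 2 concerns the start of treatment, and antibiotic exposure can change between visits, which brings the error down towards 5%. The phase figure in section 3.3 is not reproduced in the available text, so which follow-up samples enter the test cannot be seen.
- The remark in section 1.2 that communities are "relatively stable during periods of clinical stability, but differ substantially between patients" gives little support. It concerns differences in level between patients, and subtracting each patient's own baseline removes those.

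**Conclusion.** The concern does not call for a change. Its arithmetic is correct for one particular analysis: 16.6% by formula and about 16% by simulation, for five pooled changes per patient, a mean baseline, independent samples and a two-sided 5% level, with exposure fixed within the patient or a one-sample test. The protocol does not prescribe that analysis. It leaves open the unit of an unnamed non-parametric test, and the obvious ways of completing it (one summary change per patient, or one test per time point) hold the error at about 5%. Naming the test, its unit and the treatment of repeated samples is ordinary content of a statistical analysis plan, and an analyst would be expected to settle it there.
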